8.5.1.2 Noninvasive Scores of Hepatic Fibrosis

The ELF, FIB4, APRI, and NAFLD Fibrosis Score are composite indices that have been correlated with fibrosis stage in NASH study participants.²³

ELF assay, FIB4, APRI, and NAFLD Fibrosis Score use a variety of algorithms combining a number of physical attributes and biochemical and hematologic test values to determine the level of the participant's liver fibrosis (see [Appendix 9](#)). The scores will be calculated by a computerized system based on laboratory values and nonlaboratory parameters entered into the eCRF by personnel at the site. The sites will not be required to calculate scores.

Details on the collection, processing, and shipping of samples for fibrosis scoring are in the Central Pathology Manual.

- ELF assessment combines hyaluronic acid, procollagen 3 amino terminal peptide, and TIMP-1. A proprietary algorithm is used to evaluate each of these markers by immunoassay, to create an ELF Score
- FIB4 scores fibrosis by combining participant age, ALT, AST, and platelet count. The formula used to calculate the FIB4 score is provided in [Appendix 9](#)
- APRI scores fibrosis by combining AST and platelet count. The formula used to calculate the APRI Score is provided in [Appendix 9](#)
- The NAFLD Fibrosis Score scores fibrosis by combining participant age, BMI, fasting glucose, presence of diabetes, ALT, AST, platelet count, and albumin. The formula used to calculate the NAFLD Fibrosis Score is provided in [Appendix 9](#)

8.5.1.3 Imaging

All participants will have imaging performed unless imaging is contraindicated (see [Section 8.3.4](#)). Participants for whom imaging is contraindicated may still participate in the study.

Magnetic Resonance Elastography

MRE is a noninvasive medical imaging technique that measures the stiffness of soft tissues by introducing shear waves and imaging their propagation using MRI. In NASH patients, MRE is reproducible,³² and it has a higher interobserver agreement for staging fibrosis compared to histopathology.³³ Additionally, an improvement in MRE has been associated with an improvement in liver fibrosis, as observed on liver biopsy.^{32,33}

Images will be collected by the site and submitted to a central imaging vendor for evaluation. Sites should be trained and qualified before collecting study images.

Detailed instructions on the conduct of the MRE, and the acquisition and submission of MRE data to the central imaging vendor will be provided in the Imaging Manual.

The on-treatment MRE results will remain blinded to site personnel until after the study database lock. Any incidental findings of potential clinical relevance that are not directly associated with the objectives of the study should be evaluated and handled by the investigator per the site's standard of care and clinical judgment.

For participants prematurely discontinuing study medication prior to Week 24, MRE should be conducted at the ET Visit if the date of discontinuation is more than 4 weeks from the date of the previous MRE. For participants prematurely discontinuing study medication after Week 24, MRE should be conducted at the ET Visit if the date of discontinuation is more than 8 weeks from the date of the previous MRE.

Magnetic Resonance Imaging

Hepatic MRI is a noninvasive and accurate biomarker utilized for liver fat quantification. In NASH patients, MRI-PDFF accurately classifies grades and changes in hepatic steatosis,³⁰ and a $\geq 29\%$ reduction in MRI-PDFF has been associated with histological NAS improvement.³¹

Images will be collected by the site and submitted to a central imaging vendor for evaluation. Sites should be trained by the imaging vendor before collecting images.

Detailed instructions on the conduct of the MRI, and the acquisition and submission of MRI data to the central imaging vendor will be provided in the Imaging Manual.

The on-treatment MRI results will remain blinded to site personnel until after the study database lock. Any incidental findings of potential clinical relevance that are not directly associated with the objectives of the study should be evaluated and handled by the investigator per the site's standard of care and clinical judgment.

For participants prematurely discontinuing study medication prior to Week 24, MRI should be conducted at the ET Visit if the date of discontinuation is more than 4 weeks from the date of the previous MRI. For participants prematurely discontinuing study medication after Week 24, MRI should be conducted at the ET Visit if the date of discontinuation is more than 8 weeks from the date of the previous MRI.

8.5.1.5 Metabolic Assessments

Physical Metabolic Marker Assessments

Body weight, waist circumference, and BMI will be monitored as metabolic assessments.

Weight must be recorded using a calibrated scale, preferably the same scale at each clinic visit. The participant should remove shoes and heavy clothing before standing on scale.

Waist circumference will be measured at the natural waist (smallest waist circumference). If there is no natural waist, the measurement should be made midway between the iliac crest and the bottom of the rib with the measuring tape horizontal all the way around the waist. Measurement should be made at the end of normal inspiration with the participant standing. The waist measurement reported on the eCRF should represent the average of at least 2 measurements. The average measurement should agree within 1 cm. If not, additional measurement(s) should be taken.

BMI is used as an index of obesity and is a method of defining normal body weight and excess body fat. It correlates in a population with percent body fat. BMI is determined by weight (kg) divided by height (m) squared.

Note: All analysis calculations for BMI will be derived internally by the sponsor using height at Screening and weight at the specified time point.

Laboratory Metabolic Assessments

Blood will be drawn according to the Schedule of Events in [Section 1](#) for the following laboratory metabolic marker assessments. Participants should fast for at least 8 hours prior to collection of the blood samples for these assessments.

- Fasting lipids, including LDL, HDL, and TGs. The HDL/LDL ratio will be calculated using the results of these assessments
- Glucose homeostasis markers including fasting plasma glucose, fasting plasma insulin, and hemoglobin A1c

8.5.1.6 Patient-Reported Outcomes (Health-Related Quality-of-Life Questionnaires)

HRQoL questionnaires will be completed electronically by the participant and data transferred as source. Due to potential bias, the questions should not be read to the participant. Participant questionnaires will be assessed at specific visits throughout the study. See [Section 1](#) for details.

The EQ-5D-3L questionnaire (see [Appendix 6](#)) is a general quality-of-life instrument that consists of 2 components, health state description and evaluation. The health state description component measures mobility, self-care, usual activities, pain/discomfort, and anxiety/depression. Participants will rate their level of impairment in each dimension using a 3-level scale. In the evaluation component, participants evaluate their overall health status using a visual analog scale.

The SF-36 questionnaire (see [Appendix 5](#)) is a commonly used patient-reported outcome instrument used to assess quality of life. The SF-36 is a 36-question instrument, which assesses 8 health concepts: 1) limitations in physical activities because of health problems; 2) limitations in social activities because of physical or emotional problems; 3) limitations in usual role activities because of physical health problems; 4) bodily pain; 5) general mental health (psychological distress and well-being); 6) limitations in usual role activities because of emotional problems; 7) vitality (energy and fatigue); and 8) general health perceptions. Each question has 5 answers scored 1 (unable to) to 5 (no difficulty). The scale score of each

domain is calculated based on the summed score across items included in the domain and is rescaled to 0 to 100. Version 2 of the SF-36 questionnaire will be used in the study.

[figure not shown]
The CLDQ-NAFLD questionnaire²⁹ (see [Appendix 7](#)) is a disease-specific quality-of-life instrument for nonalcoholic fatty liver disease and NASH. The CLDQ-NAFLD consists of 36 items in 6 domains: abdominal symptoms, activity, emotional function, fatigue, systemic symptoms, and worry. Each item is on a Likert scale with 1 representing the most impairment and 7 representing the least impairment.

The questionnaires should be administered prior to dosing and before any other study assessments are conducted.

[figure not shown]
8.5.2 Exploratory Biomarkers

Blood samples will be collected for the assessment of exploratory biomarkers as described in [Table 8](#) in [Section 8.5.4](#). Exploratory biomarkers will include the collection of serum, plasma, [REDACTED] and whole blood, which will be used to assess markers of fibrosis and associated diseases and pathways (including cardiovascular disease, inflammation, diabetes, and liver disease as well as kidney disease and bone). Work may also include studies on the FGF21 pathway and mechanism of action as well as pathways impacted by BMS-986036. The goal is to better understand NASH and associated diseases/syndromes and the effects of BMS-986036. These studies may include, but are not limited to, assessments listed in Table 8 in Section 8.5.4.

- PRO-C3

- Metabolic biomarkers such as adiponectin

- Serum and plasma biomarkers associated with drug target pathway or pathways impacted by target, liver disease, NASH, fibrosis, apoptosis, diabetes mellitus, metabolic syndrome, inflammation, kidney and bone. Biomarkers may include but are not limited to cluster of differentiation 163 (CD163), C-reactive protein (CRP), pulmonary and activation-regulated cytokine, TIMP-1 and plasminogen activator inhibitor 1 (PAI-1)

- Blood (serum or plasma) samples to develop new or improved assays for pathway and functional markers associated with either the target, fibrosis, NASH, liver or drug
- Ribonucleic acid (RNA) from whole blood and from liver biopsies (when available), for broad gene expression profiling and directed gene analyses. Common RNA technologies may be employed, including but not limited to quantitative polymerase chain reaction, hybridization microarrays, and RNA sequencing. The sponsor has in place a system for restricting access to RNA sequencing data such that only gene expression data are made available

- Micro RNA (miRNA)

Information on the collecting, processing, and submission of samples to the central laboratory are in the Study Laboratory Manual.

8.5.3 Safety Assessments

Planned time points for all safety assessments are listed in the Schedule of Activities (Section 1). All urgent safety concerns must be discussed with the sponsor immediately upon occurrence or awareness to determine if the participant should continue or discontinue treatment.

Safety will be assessed using incidence of all AEs; the incidence of SAEs; the incidence of AEs leading to withdrawal of study medication; the incidence of AEs of special interest, immunogenicity, laboratory data, ECG monitoring, physical examinations, and monitoring of BMD via DXA.

8.5.3.1 Adverse Events

The definitions of an AE or SAE can be found in [Appendix 8](#).

AEs will be reported by the participant (or, when appropriate, by a caregiver, surrogate, or the participant's legally authorized representative).

The investigator and any designees are responsible for detecting, documenting, and reporting events that meet the definition of an AE or SAE and remain responsible for following up AEs that are serious, considered related to the study medication or the study, or that caused the participant to discontinue before completing the study.

For weight change (increase or decrease) to be considered an AE, the change should be 10% or more from Baseline that cannot be explained by lifestyle modifications alone.

Contacts for SAE reporting are specified in [Appendix 8](#).

Time Period and Frequency for Collecting AE and SAE Information

Sections 5.6.1 and 5.6.2 in the IB represent the Reference Safety Information to determine expectedness of SAEs for expedited reporting.

The collection of nonserious AEs should begin at initiation of study medication and continue until the Week 52/PTFU Visit ([Section 1](#)).

Following the participant's written consent to participate in the study, all SAEs, whether related or not related to study medication, must be collected, including those considered by the investigator to be related to study medication or protocol-specified procedures. All SAEs will be collected through the Week 52/PTFU Visit and will be reported as described in [Appendix 8](#).

The investigator must report any SAE occurring after the Week 52/PTFU Visit that is believed to be related to study medication or a protocol-specified procedure.

- Medical occurrences that begin before the start of study medication but after obtaining informed consent will be recorded on the appropriate section of the eCRF
- All SAEs will be recorded and reported to sponsor or designee within 24 hours, as indicated in [Appendix 8](#)
- The investigator will submit any updated SAE data to the sponsor or designee within 24 hours of this information being available

Investigators are not obligated to actively seek AEs or SAEs in former study participants. However, if the investigator learns of any SAE, including a death, at any time after a participant has been discharged from the study, and he/she considers the event reasonably related to the study medication or study participation, the investigator must promptly notify the sponsor.

The method of evaluating intensity and assessing causality of AEs and SAEs and the procedures for completing and reporting/transmitting SAE reports are provided in [Appendix 8](#).

Method of Detecting AEs and SAEs

AEs can be spontaneously reported or elicited during open-ended questioning, examination, or evaluation of a participant. Care should be taken not to introduce bias when collecting AE and/or SAEs. Inquiry about specific AEs should be guided by clinical judgment in the context of known AEs, when appropriate for the program or protocol.

Follow-Up and Recording of AEs and SAEs

- Nonserious AEs should be followed to resolution or stabilization, or reported as SAEs if they become serious (see [Appendix 8](#))

- Follow-up is also required for nonserious AEs that cause interruption or discontinuation of study medication and for those present at the end of study medication, as appropriate
- All nonserious AEs and SAEs must be recorded and described on the corresponding pages of the eCRF. Completion of supplemental eCRFs may be requested for AEs/SAEs and/or laboratory abnormalities that are reported/identified during the course of the study

After the initial AE/SAE report, the investigator is required to proactively follow each participant at subsequent visits/contacts. All SAEs and nonserious AEs of special interest (as defined in [Section 8.5.3.7](#)) will be followed until resolution, until the condition stabilizes, until the event is otherwise explained, or until the participant is lost to follow-up (as defined in [Section 8.3.9.3](#)).

Further information on follow-up procedures is given in [Appendix 8](#).

Regulatory Reporting Requirements for SAEs

- Prompt notification by the investigator to the sponsor of SAEs is essential so that legal obligations and ethical responsibilities towards the safety of participants and the safety of a product under clinical investigation are met
- An investigator who receives an investigator safety report describing SAEs or other specific safety information (e.g., summary or listing of SAEs) from the sponsor will file it along with the IB and will notify the IRB/IEC, if appropriate according to local requirements

Sponsor or designee will be reporting AEs to regulatory authorities and IRB/ECs according to local applicable laws including European Directive 2001/20/EC and FDA Code of Federal Regulations 21 CFR Parts 312 and 320. A suspected unexpected serious adverse reaction is a subset of SAEs and will be reported to the appropriate regulatory authorities and investigators following local and global guidelines and requirements.

Pregnancy

Urine or serum samples will be collected at each visit through the Week 52/PTFU Visit for pregnancy testing for WOCBPs. A negative serum pregnancy test is required during Screening. After the Screening Period, urine pregnancy testing will be conducted instead of serum testing at any site where it is allowed by the IRB/EC overseeing study conduct at that site.

Investigators shall counsel WOCBPs on the importance of pregnancy prevention and the implications of an unexpected pregnancy. Investigators shall advise on the use of highly effective methods of contraception (i.e., those that have a failure rate of < 1% when used consistently and correctly as discussed in [Appendix 2](#)).

If, following initiation of the study medication, it is subsequently discovered that a participant is pregnant or may have been pregnant at the time of study exposure, including during at least 5 half-lives after product administration (5 days) plus 30 days (duration of

ovulatory cycle) for a total of 35 days after the end of the Double-Blind Treatment Period, the investigator must immediately notify the sponsor medical monitor/designee of this event and complete and forward a Pregnancy Surveillance Form to the sponsor designee within 24 hours of awareness of the event and in accordance with SAE reporting procedures described in [Appendix 8](#).

The study medication will be permanently discontinued in an appropriate manner (e.g., dose tapering if necessary for participant safety). Please call the sponsor medical monitor within 24 hours of awareness of the pregnancy.

Follow-up information regarding the course of the pregnancy, including perinatal and neonatal outcome and, where applicable, offspring information must be reported on the Pregnancy Surveillance Form ([Appendix 2](#)).

Any pregnancy that occurs in a female partner of a male study participant should be reported to sponsor or designee during at least 5 half-lives after product administration (5 days) plus 30 days (duration of ovulatory cycle) for a total of 35 days after the end of the Double-Blind Treatment Period. In order for the sponsor or designee to collect any pregnancy surveillance information from the female partner, the female partner must sign an ICF for disclosure of this information. Information on this pregnancy will be collected on the Pregnancy Surveillance Form.

Laboratory Test Result Abnormalities

The following laboratory test result abnormalities should be captured on the nonserious AE eCRF page or SAE eCRF page, as appropriate. Paper forms are to be used only in the event that the electronic system is not functioning.

- Any laboratory test result that is clinically significant or meets the definition of an SAE
- Any laboratory test result abnormality that required the participant to have study medication discontinued or interrupted
- Any laboratory test result abnormality that required the participant to receive specific corrective therapy

It is expected that wherever possible, the clinical rather than laboratory term would be used by the reporting investigator (e.g., anemia versus low hemoglobin value).

Potential Drug-Induced Liver Injury

Wherever possible, timely confirmation of initial liver-related laboratory abnormalities should occur prior to the reporting of a potential DILI event. All occurrences of potential DILIs, meeting the defined criteria, must be reported as SAEs (see Appendix 8 for reporting details). **Repeat laboratory testing may be performed locally**, and the results should be promptly communicated to the investigator site.

For the purpose of evaluating a potential DILI, the Baseline value is defined as the mean of the test results from analysis of samples collected during Screening and on Day 1.

Note that the evaluation processes below do not replace SAE reporting per defined criteria in [Appendix 8](#).

Evaluation of Participants with New Elevations of Aminotransferases and/or Total Bilirubin

Repeat laboratory testing (including ALT, AST, fractionated bilirubin and alkaline phosphatase) and physical examination should be performed within 48-72 hours when:

- Participants with normal Baseline aminotransferase (ALT and/or AST) values develop elevations greater than $3\times$ the ULN based upon the central lab, or
- Participants with elevated Baseline aminotransferase values experience additional increases greater than $2\times$ the Baseline (with concomitant elevations of total bilirubin $> 2\times$ ULN) **AND** ALT and/or AST is > 200 U/L.

If the new elevations in aminotransferases persist and the participant is symptomatic, then the drug should be discontinued, and the participant should be evaluated for other causes of liver injury or disease. The medical monitor should be contacted within 48-72 hours.

If the participant is asymptomatic, the participant should be placed under “close observation”, defined as physical examination and laboratory evaluation 2-3 times per week.

If close observation is not possible, study medication should be discontinued. The frequency of retesting can decrease to once a week or less if abnormalities stabilize or the study medication has been discontinued and the participant is asymptomatic.

Discontinuation or Temporary Interruption of Study Medication

In addition to the reasons for discontinuation described above, study medication should be discontinued or temporarily interrupted if either of the 2 following scenarios occur:

1) Aminotransferases (ALT and/or AST) $> 2\times$ Baseline and aminotransferases $> 3\times$ ULN **and** either:

- i. the increase is accompanied by a concomitant increase in total bilirubin to $> 2\times$ Baseline **OR** the INR concomitantly increases by > 0.2 ;

OR

- ii. there are concomitant signs and symptoms of new-onset fatigue, nausea, vomiting, right upper quadrant pain or tenderness, fever, rash, and/or eosinophilia ($> 5\%$).

2) Total bilirubin increases to $> 2\times$ ULN **AND**:

- i. there are concomitant signs and symptoms of new-onset fatigue, nausea, vomiting, right upper quadrant pain or tenderness, fever, rash, and/or eosinophilia ($> 5\%$).

If the above rule is met, a potential DILI work up for competing etiologies (e.g., alcohol use, viral hepatitis, biliary obstruction, autoimmune liver disease) must be performed, and a complete liver profile including INR must be repeated within 48-72 hours. **The medical monitor should be contacted within 48-72 hours.** Study medication can be restarted only if an alternative etiology is definitively identified and liver tests (aminotransferases, total bilirubin and/or INR) have returned to Baseline.

Other Safety Considerations

Any significant worsening noted during interim or final physical exams, ECGs, or any other potential safety assessments required or not required by protocol should also be recorded as a nonserious AE or SAE, as appropriate, and reported accordingly. ECGs will be read and interpreted at the site or by a local reader.

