8.3.9 Withdrawal of Participants

8.3.9.1 Discontinuation of Study Medication

Participants MUST discontinue investigational product (IP) (and non-investigational product [non-IP] at the discretion of the investigator) for any of the following reasons.

- Participant's request to stop study medication. Participants who request to discontinue study medication will be expected to complete an ET Visit and subsequent follow-up visits/procedures per the Schedule of Activities (e.g., Week 52/PTFU; Section 1). The only exception to this is when a participant specifically withdraws consent for any further contact with him/her or persons previously authorized by participant to provide this information. Participants' withdrawal of consent should be explained in detail in the medical records by the investigator as to whether the withdrawal is from further treatment with study medication only or also from study procedures and/or ET, Week 52/PTFU Visit, etc. (see [Section 8.3.9.2](#))
- Any clinical AE, laboratory abnormality or intercurrent illness, which, in the opinion of the investigator, indicates that continued participation in the study is not in the best interest of the participant
- The participant experiences a major bone fracture or is diagnosed with osteoporosis that requires treatment
- Abnormal liver tests as defined in [Section 8.5.3.1](#)
- On 2 consecutive visits (at least 2 weeks apart), a participant has an eGFR < 30 mL/min/1.73 m², according to the *Modification of Diet in Renal Disease Study* equation
- If there is a significant protocol violation. The violation should be discussed with the medical monitor prior to discontinuing study medication
- Loss of ability to freely provide consent through imprisonment or involuntary incarceration for treatment of either a psychiatric or physical (e.g., infectious disease)

illness (Note: Under specific circumstances, a participant who has been imprisoned may be permitted to continue as a participant. Strict conditions apply, and sponsor approval is required.)

- The participant becomes pregnant (study medication must be discontinued immediately)

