In the case of pregnancy (see [Section 8.5.3.1](#)), the investigator must immediately notify the medical monitor or designee of this event. In the event a participant becomes pregnant during a clinical study, the study medication must be discontinued immediately. In most cases, the study medication will be permanently discontinued in an appropriate manner. The medical monitor should be contacted within 24 hours of awareness of the pregnancy
- Termination of the study or program by the sponsor
- If a participant loses more than 10% of their total body weight, the investigator should contact the medical monitor. The investigator, together with the medical monitor, will then determine whether the participant should continue to take study medication

If study medication is discontinued prior to the participant's completion of the study, the reason for the discontinuation must be documented in the participant's medical records and entered on the appropriate eCRF page. The discontinuation should also be reported via the IRT. As indicated, appropriate follow-up and/or alternate medical care must be arranged for the participant. Please notify the medical monitor as soon as possible when discontinuation of study medication is being considered.

See [Section 8.4.6](#) for details regarding dose modification and/or treatment interruption.

Participants who prematurely discontinue study medication will be expected to complete an ET Visit and subsequent follow-up visits/procedures per the Schedule of Activities, including a Week 52/PTFU Visit ([Table 2](#) in [Section 1](#)), DXA and Immunogenicity Follow-Up Visits ([Table 3](#) in [Section 1](#)) (see [Section 8.5.3.6](#)). The only exception to this requirement is when consent is withdrawn for all study procedures or the participant loses the ability to consent freely (i.e., is imprisoned or involuntarily incarcerated for the treatment of either a psychiatric or physical illness). Participants who discontinue study medication will not be replaced (see [Section 8.3.9.4](#)).

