8.4.2 Study Medication Administration

Participants should be instructed to make every effort to administer study medication on the same day each week at approximately the same time of day. Each weekly administration will consist of 2 SC injections.

On Day 1 and at the Week 4, 8, 12, 16, 20, 24, 32, and 40 Visits, study medication will be self-administered by the participant or administered by their designee at the study site as part of the participant's scheduled study visits. At those visits, study medication dosing should be held until all study-related assessments, including participant questionnaires, vital signs, ECG, AE evaluation, physical examinations, and laboratory sample collection (including trough [predose] PK) have been completed. [REDACTED]

[REDACTED] If a study visit occurs on a day that is not a planned dosing day, the participant should continue to administer the medication on the planned dosing day; all study-related assessments will continue to be performed at the planned study visit (in-clinic administration of study drug would not occur). [REDACTED]

[REDACTED]

Study medication is blinded and is supplied in a pre-filled syringe. Each participant will be dispensed a treatment kit containing 2 smaller boxes (for each weekly administration). Each smaller box will contain 1 pre-filled syringe of the medication. Both syringes will be administered in the abdominal area at different locations per training guidelines. Study medication will be assigned by the IRT system.

Guidance and training on administration should be given to the participant (or caregiver, if applicable) prior to the first administration. At a minimum, the first administration should be done by the participant under the supervision of qualified site personnel. Training may be repeated as necessary at any study visit at the discretion of the investigator to maintain treatment compliance. When injections are administered at the site during study visits, site staff may observe the injection to ensure proper technique is being employed. Participants will be required to capture the date, time, and location of each injection on the supplied study medication administration card.

Specific instructions for study medication administration as well as training materials for participants (or caregivers, if applicable) are in the Pharmacy Manual.

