8.4.6 Dose Modification

8.4.6.1 Modification of Dose

No dose reductions or modifications are allowed. If a participant interrupts treatment due to an AE, study medication may be restarted after consultation with the medical monitor.

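### On pregnancy, Protocol 8.3.9.1 requires an immediate stop, 8.5.3.1 permits tapering and 8.4.6.1 bars dose reduction; the first two also differ on whether stopping is always permanent

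*Protocol*

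**What the plan says.** Protocol 8.3.9.1 (Discontinuation of Study Medication) lists pregnancy among the reasons for which participants must stop: "The participant becomes pregnant (study medication must be discontinued immediately". The text below the list repeats the rule and then adds a qualification: "the study medication must be discontinued immediately. In most cases, the study medication will be permanently discontinued in an appropriate manner". It does not mention tapering.

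Protocol 8.5.3.1 (Adverse Events, under Pregnancy) covers the same event: "The study medication will be permanently discontinued in an appropriate manner (e.g., dose tapering if necessary for participant safety". Here the stop is permanent without qualification, nothing says it must be immediate, and tapering is offered as an example.

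Protocol 8.4.6.1 (Modification of Dose) states "No dose reductions or modifications are allowed" and makes no exception for pregnancy.

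On supply, Protocol 8.4.2 says "Study medication is blinded and is supplied in a pre-filled syringe" and "Each smaller box will contain 1 pre-filled syringe of the medication". Table 6 fixes two 1 mL syringes per week for each arm, and the IRT assigns the kits. No taper regimen appears.

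**The concern.** A taper means giving at least one more dose after the pregnancy is known. That cannot be squared with an immediate stop, and a reduced dose cannot be squared with a ban on dose reductions. The section a site is most likely to open when a pregnancy is reported is the one headed Pregnancy, and that is the version without the word immediately.

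The second disagreement is about permanence. Section 8.3.9.1 leaves room for cases in which the stop is not permanent, without saying which. Section 8.5.3.1 leaves none.

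What is at stake is the safety instruction for a participant whose event the protocol handles under its serious adverse event procedures. Two sites could act differently, each in good faith and each able to cite the protocol. No estimate, test or sample size depends on it.

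**Working it through.** No arithmetic applies: the point depends on no rate, sample size or error level. The check is to set the texts side by side on four questions.

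1. **Must the stop be immediate?**
   - 8.3.9.1: yes, stated in the list and again in the text ("In the event a participant becomes pregnant during a clinical study, the study medication must be discontinued immediately").
   - 8.5.3.1: not stated.
   - 8.4.6.1: silent.

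2. **May the dose be tapered?**
   - 8.3.9.1: not mentioned, and excluded in effect, because a taper requires further doses.
   - 8.5.3.1: yes, if participant safety needs it.
   - 8.4.6.1: no dose reduction in any circumstance. The section does allow restarting after an interruption for an adverse event, following consultation with the medical monitor, but at no altered dose.

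3. **Is the stop always permanent?**
   - 8.3.9.1: usually ("In most cases, the study medication will be permanently discontinued in an appropriate manner").
   - 8.5.3.1: yes, without qualification.

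4. **Is a taper described anywhere in the drug supply?** Table 5 lists 10 mg/mL, 20 mg/mL and placebo syringes. Table 6 assigns a fixed weekly pair to each arm:
   - 10 mg arm: one 10 mg syringe and one placebo
   - 20 mg arm: one 20 mg syringe and one placebo
   - 40 mg arm: two 20 mg syringes
   - placebo arm: two placebo syringes

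   Section 8.4.2 has both syringes given each week, and 8.4.4.1 says all syringes look alike. Sections 8.4 to 8.4.4.1 and the SAP contain no taper schedule, taper kit or IRT step-down.

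On questions 1 and 2, 8.3.9.1 and 8.5.3.1 cannot both be followed if a site chooses to taper, and 8.4.6.1 would be breached as well. On question 3 the two pregnancy texts differ in scope. On question 4 the permission in 8.5.3.1 has no described means of being carried out.

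The safeguards bear on how far this could go. Both 8.3.9.1 and 8.5.3.1 require the medical monitor to be told at once and contacted within 24 hours of the site learning of the pregnancy. Dosing is weekly, so that contact will usually come before the next dose, though not necessarily when the pregnancy is found on a dosing day. Section 8.4.4.2 names pregnancy as a ground on which the investigator may break the blind when knowing the treatment is critical to managing the participant.

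**The case against.** The strongest reply is that no site would act on the taper wording. It is an example, conditional on participant safety, and reads like general language carried over from other protocols. Section 8.3.9.1 states the immediate stop twice under a mandatory heading, and a site tapering on its own authority would have to bypass the medical monitor. This stands as a reason to expect few or no actual cases. It does not remove the conflict, because the monitor works from the same text and nothing says which section governs.

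Four stronger readings are tempting, and the documents do not support them.

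- A reader might infer that a tapering site could not find out what dose it was giving. Section 8.4.4.2 lets the investigator unblind through the IRT in pregnancy without first asking the sponsor.
- A reader might infer that the Early Termination Visit depends on which section is read. Both sections discontinue study medication. Section 8.1 places that visit at discontinuation, and 8.3.9.1 expects it of everyone who stops early unless consent is withdrawn or can no longer be freely given.
- A reader might work out the dose delivered by giving one of the two syringes. No section offers that as a taper, and 8.4.2 has both given, so such figures would measure an act the protocol does not describe.
- A reader might conclude that tapering is physically impossible. It is undescribed, which is a weaker statement: the Pharmacy Manual and IRT Manual are not in view, and a 10 mg/mL syringe is a listed product.

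It is also fair to say that this is an inconsistency of text and that the trial's design does not turn on it. Protocol 6.2 records that enrollment had closed with 197 randomized, so the wording matters only for women of childbearing potential still receiving study medication.

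**Conclusion.** The point holds as a contradiction between instructions. Sections 8.3.9.1 and 8.5.3.1 disagree on whether stopping must be immediate and whether it is always permanent. The taper allowed by 8.5.3.1 is barred by 8.4.6.1 and has no described means of supply. A site following 8.5.3.1 could give further doses after 8.3.9.1 requires a stop.

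Its reach is small. That few participants would be affected is an assumption, since the documents give no expected number of pregnancies. The risk for any one of them is lowered by the 24-hour contact and the option to unblind. There is no effect on sample size, power, error rates or analyses. It should still be corrected, because it is a safety instruction that cannot be followed as written in all its parts, and correcting it costs almost nothing.

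The conclusion rests on the protocol and SAP alone. A manual that describes a taper would change the supply observation but not the conflict among the three sections.

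**What to change.** Reconcile 8.3.9.1, 8.5.3.1 and 8.4.6.1 into one pregnancy instruction, stated once and cross-referenced from the other two sections. It should settle two things:

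- whether tapering is permitted at all, given the dose-modification rule and the fixed weekly syringes;
- whether discontinuation is always permanent and, if not, in which cases.

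Delete whatever wording conflicts with the sponsor's choice. If a taper is retained, 8.4.6.1 needs a stated exception and the supply sections need to say how it would be carried out. Which clinical rule applies is for the sponsor to decide.

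The cost is the deletion or rewording of one or two sentences in an amendment or a letter to sites, somewhat more if a taper is kept. Nothing changes in the sample size, the SAP or the planned analyses.
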